4.9.2 Caspofungin with Option for Oral Step-Down Regimen of Fluconazole

Treatment regimens with caspofungin and fluconazole are consistent with standard of care regimens in approved labeling ([Cancidas \[caspofungin acetate\] Prescribing Information](#); [Diflucan \[fluconazole\] tablets Prescribing Information](#)).

4.10 Population to be Studied

Adult subjects with candidemia and/or invasive candidiasis.

4.11 Rationale for Use of Rezafungin for Injection in Candidemia and Invasive Candidiasis

Candidemia is a fungal bloodstream infection usually affecting patients who are already ill with other comorbidities. Invasive candidiasis defines a number of different organ-specific infections with *Candida* spp. Candidemia and invasive candidiasis may present without the other syndrome or may exist together as part of the same pathophysiology of disseminated candidiasis. Risk factors for candidemia and invasive candidiasis include recent surgery, organ and bone marrow transplants, broad-spectrum antibiotic use, receipt of total parenteral nutrition, end stage renal disease, indwelling vascular catheters or other devices, etc. While candidemia is often associated with other forms of invasive candidiasis, including intra-abdominal abscess, peritonitis, or pleuritic involvement, candidemia without other overt organ involvement is the most common form of invasive candidiasis diagnosed. A recent study by the ESCMID Fungal Infection Study Group reported the incidence of candidemia as 6.9 per 1000 intensive care unit (ICU) patients with mortality rates between 20% and 49% (Kett 2011; Gudlaugsson 2003; Arendrup 2011). Candidemia and invasive candidiasis are serious and potentially life-threatening infectious complications that require aggressive and timely antifungal management.

The current IDSA and ESCMID guidelines recommend echinocandins as first-line therapy for candidemia and most forms of invasive candidiasis (Pappas 2016; Cornely 2012). There are currently 3 commercially authorized echinocandins in the US and the European Union: caspofungin, micafungin, and anidulafungin. These echinocandins are administered once daily via IV infusion and share similar PK parameters and safety profiles. Rezafungin is a novel echinocandin derived from another echinocandin (anidulafungin). Rezafungin has a more stable molecular structure compared to the other echinocandins, which results in a reduction in the formation of toxic metabolites and an improvement in the duration of exposure to active drug. This stability further translates into a potentially improved safety profile as demonstrated in both nonclinical and clinical studies, as well as a unique PK profile that allows for high dose, front-loaded exposures for improved fungal killing and once weekly IV dosing.

Both in vitro and in vivo data have demonstrated the potency and efficacy of rezafungin against *Candida* and disseminated candidiasis (Section 4.1 and Investigator's Brochure). In all nonclinical efficacy studies performed for Rezafungin in neutropenic disseminated candidiasis, rezafungin has performed as well as, or better than, currently approved echinocandin comparators. Furthermore, nonclinical data indicate the exposure of rezafungin is substantially higher in infected tissues compared to other echinocandins, indicating the potential to improve outcomes in invasive candidiasis (Zhao 2017). The completed Part A of the Phase 2 study demonstrated efficacy for Rezafungin for Injection comparable to standard of care at Day 14 for all endpoints. The Rezafungin for Injection regimen starting with a 400 mg once weekly loading dose followed by 200 mg once weekly for a total of 2 to 4 doses, had robust results for the primary endpoint of overall success compared with standard of care (Rezafungin for Injection, 71.0%; caspofungin, 64.3%). Additionally, the Phase 2 results for Part A also indicated that Rezafungin for Injection appears to be well-tolerated at 400 mg once weekly and at 400 mg

loading dose Week 1 followed by 200 mg once weekly. In PK and PD models, the proposed Rezafungin for Injection dosing regimens for this Phase 3 study demonstrate 100% target attainment of wild-type *C. albicans* and *C. glabrata* (*C. albicans* data is presented in [Section 4.9](#)). The duration of antifungal therapy in standard practice depends on the time it takes to clear the *Candida* from infected blood or tissues, and thus patients with invasive candidiasis often require a longer duration of therapy than patients with candidemia alone. To that end, all subjects in this study must be administered study drug for at least 14 days followed by an optional third or fourth week of treatment if clinically indicated.

This Phase 3 study is intended to confirm the efficacy and safety of Rezafungin for Injection administered at 400 mg loading dose in Week 1 followed by 200 mg once weekly for the treatment of patients with candidemia and/or invasive candidiasis.

4.12 Statement of Compliance

This study will be conducted in compliance with the protocol, Good Clinical Practice (GCP), the ethical principles of the Declaration of Helsinki, and applicable regulatory and Institutional Review Board (IRB) or Independent Ethics Committee (IEC) requirements.

5.0 STUDY OBJECTIVES

The primary objectives of this study are to:

- Demonstrate that Rezafungin for Injection is non-inferior to caspofungin for all-cause mortality (ACM) at Day 30 (-2 days) in the modified intent-to-treat (mITT) population (US Food and Drug Administration [FDA] primary objective)
- Demonstrate that Rezafungin for Injection is non-inferior to caspofungin for global cure (clinical cure as assessed by the Investigator, radiological cure [for qualifying invasive candidiasis subjects], and mycological eradication, as confirmed by the Data Review Committee [DRC]) at Day 14 (± 1 day) in the mITT population (European Medicines Agency [EMA] primary objective)

The secondary objectives of this study are to:

- Compare global cure (clinical cure as assessed by the Investigator, radiological cure [for qualifying invasive candidiasis subjects], and mycological eradication, as confirmed by the DRC) for subjects receiving Rezafungin for Injection and caspofungin at Day 5, Day 30 (-2 days), End of Treatment (EOT) (≤ 2 days of last dose), and Follow-up (Days 52–59) in the mITT population
- Compare mycological eradication for subjects receiving Rezafungin for Injection and caspofungin at Day 5, Day 14 (± 1 day), Day 30 (-2 days), EOT (≤ 2 days of last dose), and Follow-up (Days 52–59) in the mITT population
- Compare clinical cure as assessed by the Investigator for subjects receiving Rezafungin for Injection and caspofungin at Day 5, Day 14 (± 1 day), Day 30 (-2 days), EOT (≤ 2 days of last dose), and Follow-up (Days 52–59) in the mITT population
- Compare radiological cure for invasive candidiasis subjects receiving Rezafungin for Injection and caspofungin at Day 5, Day 14 (± 1 day), Day 30 (-2 days), EOT (≤ 2 days of last dose), and Follow-up (Days 52–59) in the mITT population
- Compare the safety and tolerability for subjects receiving Rezafungin for Injection and caspofungin in the safety population
- Evaluate the PKs of Rezafungin for Injection

An exploratory objective of this study is to:

- Compare resolution of systemic signs attributable to candidemia and/or invasive candidiasis for subjects receiving Rezafungin for Injection and caspofungin at Day 5, Day 14 (± 1 day), Day 30 (-2 days) and Follow-up Days (52–59) in the mITT population

6.0 STUDY DESIGN

6.1 Description of the Study

The study design figure is provided in [Figure 1](#). The Schedule of Assessments and Procedures for the Required Treatment, EOT, and Follow-up Periods is presented in [Table 1](#) and the Schedule of Assessments and Procedures for the Optional Treatment Period is presented in [Table 2](#).

This is a Phase 3, multicenter, prospective, randomized, double-blind, efficacy and safety study of Rezafungin for Injection (IV) versus a comparator regimen of caspofungin (IV) followed by optional oral fluconazole step-down therapy in subjects with candidemia and/or invasive candidiasis. Subjects will be randomly assigned (1:1 ratio) to receive either Rezafungin for Injection or caspofungin. After ≥ 3 days IV treatment (or the minimum duration of IV therapy advised by the site's national/regional/local guidelines, whichever is greater), subjects may be switched to oral step-down therapy by the Investigator if they meet the oral step-down therapy criteria.

6.1.1 Subjects Randomized to Rezafungin for Injection

Subjects randomized to Rezafungin for Injection will receive a 400 mg loading dose in Week 1, followed by 200 mg once weekly, for a total of 2 to 4 doses. To maintain the blind, subjects will also receive daily placebo to match for caspofungin IV, which will be administered on Days 2–7, Days 9–14, and during the optional dosing period on Days 16–21 and Days 23–28, or will receive daily placebo for oral step-down therapy (first eligibility on Day 4 or later as advised by a site's national/regional/local guidelines), which will be administered every day including rezafungin infusion days (see [Figure 1](#) and [Figure 2](#)).

6.1.2 Subjects Randomized to Caspofungin

Subjects randomized to caspofungin will receive a total treatment of ≥ 14 days beginning with a single caspofungin 70 mg IV loading dose on Day 1, followed by caspofungin 50 mg IV once daily with the option to continue treatment ≤ 28 days. After ≥ 3 days (or the minimum duration of IV therapy advised by the site's national/regional/local guidelines, whichever is greater) of caspofungin treatment, subjects who meet the oral step-down therapy eligibility criteria (see [Section 8.2.3.3](#)) may be switched to oral fluconazole at a dose of 6 mg/kg administered once daily (rounded to the nearest 200 mg increment) with a maximum daily dose of 800 mg (e.g., a subject weighing 73 kg would receive fluconazole 400 mg dose [2 capsules of 200 mg each] based on a 6 mg/kg target dose [$73 \text{ kg} \times 6 \text{ mg/kg} = 438 \text{ mg}$]). NOTE: Refer to dosing section for alternative regimens of fluconazole in subjects with renal impairment in [Section 8.2.3.5](#)). To maintain the blind, subjects in the caspofungin treatment group who have switched to oral step-down therapy will receive matching IV placebo for Rezafungin for Injection once weekly on the days of scheduled Rezafungin for Injection doses until study drug is stopped (Day 8; Day 15 [if applicable] and Day 22 [if applicable]) (see [Figure 1](#) and [Figure 2](#)).

6.1.3 End of Treatment Visit and Follow-up Visits

Subjects will complete an EOT visit within 2 calendar days after the last dose of study drug, and a Follow-up visit within the Day 52–59 period. Subjects who stop study drug prior to Day 22 AND are considered clinical failures (i.e., require a change in antifungal therapy to treat candidemia and/or invasive candidiasis) may have their Follow-up visit earlier, but the visit must still be ≥ 30 days following the last once weekly infusion of Rezafungin for Injection/placebo (i.e., Day 1, Day 8, Day 15, or Day 22).

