An insufficient therapeutic effect may be determined prior to the planned duration of therapy in the study. This determination will require an assessment of clinical status including the synthesis of symptoms and signs data (both local and systemic). Subjects who are deemed to have an insufficient therapeutic effect should be discontinued from study drug therapy.

If a subject has daily blood cultures positive for *Candida* spp. through Day 7 despite appropriate study drug administration, this should be considered an insufficient therapeutic effect and study drug should be discontinued and salvage therapy initiated. The subject should remain in the study through the Follow-up visit (Days 52–59) to complete safety assessments and assess for mortality.

Seven days is the maximum number of daily positive blood cultures allowed prior to a change in antifungal therapy. The Investigator may determine that there is an insufficient therapeutic response prior to Day 7.

- Investigator discretion
 - Resistant Pathogen(s): In the event an organism resistant to ≥ 1 of the potential study drugs is isolated, the Investigator will determine whether the subject remains on study drug therapy. The Investigator may decide to continue study drug therapy if, in the Investigator's opinion, there is clear and continuing clinical improvement while on therapy.
 - The Investigator may decide to prematurely discontinue study drug therapy and to initiate an alternative and appropriate therapy if, in the Investigator's opinion, the subject is not benefiting from study drug.

NOTE: The Medical Monitor should be contacted to discuss whether to continue or prematurely discontinue a subject on the study drug in the event the subject requires systemic concomitant antifungal therapy.

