13.4.4 Additional Efficacy Analyses

The number and percentage of subjects with resolution of all systemic signs attributable at baseline to candidemia and/or invasive candidiasis at Day 5, Day 14 (± 1 day), Day 30 (-2 days) and Follow-up (Days 52–59) will be presented by treatment group in the mITT population.

The number and percentage of subjects who died up through the Follow-up visit (ACM) will be presented by treatment group in the mITT population. In addition, Kaplan-Meier (KM) methods will be utilized to analyze survival time in the mITT and ITT populations. Subjects who remain alive or are lost to follow-up will be censored at the last date known to be alive. Kaplan-Meier survival curves will be provided. The 25th, 75th percentiles and the median survival time as well as the probability of being alive at Day 5, Day 14, Day 30, and Day 55 will be determined by treatment group.

The time to the first negative blood culture (for those subjects enrolled with a positive blood culture) without subsequent positive culture from a sample drawn following the first dose of study drug will be summarized using KM methods. Subjects will be censored if they receive an alternative antifungal (i.e., other than study drug) for the treatment of the candidemia, died or were lost to follow up prior to having the negative blood culture. Kaplan-Meier survival curves will be provided. The 25th, 75th percentiles and the median survival time will be determined by treatment group.

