2.3.2. All-Cause Mortality (ACM) through the FU Visit

All-cause mortality through the FU Visit (Day 59) is defined as death due to any cause from the date and time of first dose of treatment through the FU Visit. Subjects who did not die or died after Day 59 or are lost to follow-up will be censored in the analysis at the last date known to be alive or Day 59, whichever is earlier.

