4.3.4. Additional Efficacy Outcomes

Analyses for the additional efficacy endpoints will be performed using the mITT population.

Resolution of all systemic signs attributable at baseline to candidemia and/or invasive candidiasis for subjects receiving of Rezafungin for Injection and caspofungin at Day 5, Day 14 (± 1 day), Day 30 (-2 days) and Follow-up (Days 52-59) will be presented by treatment group. This analysis will be repeated for subjects additionally with mycological eradication.

All-cause mortality at Follow-up will be presented for the mITT population by treatment group using frequencies and percentage of subjects that were alive and deceased at Follow-up. In addition, Kaplan-Meier (KM) methods will be utilized to analyze survival time in the mITT and ITT populations. The probability of being alive at Day 5, Day 14, Day 30, and Day 55 will be determined by treatment group. In addition, the 25th, 50th (median), and 75th percentiles will be provided by treatment group. The number and percentage of subjects censored will be provided. KM survival curves will be provided. The number of subjects at risk and number died in each treatment group will be displayed below the x-axis at day= 0, 5, 14, 30, 55. Survival status will be provided in a by-subject listing.

The time to the first negative blood culture without subsequent positive culture from a sample drawn following the first dose of study drug will be summarized using KM methods for mITT population. The calculation will be in reference to the first dose date. For subjects who have negative blood culture prior to the first dose of study drug without subsequent positive culture, the time to the first negative blood culture will be set to zero. A log-rank test will be performed to test for differences in survival curves between treatment groups. Subjects will be censored if they receive an alternative antifungal (i.e., other than study drug) for the treatment of the candidemia, died or were lost to follow up prior to having the negative blood culture (see Section 2.3.3). KM survival curves will be provided. The 25th, 75th percentiles and the median survival time and 95% CIs will be determined by treatment group. This analysis will be repeated for the following subsets among the subjects with any post-baseline blood cultures: 1) Subjects with

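### Clinical failures may have Follow-up as early as Day 31 with no later vital-status contact specified, so survival estimates after Day 30 can be censored by outcome, and Protocol 6.1.3 and 7.4.2 disagree on how long such subjects are followed

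*Protocol*

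**What the plan says.** Under Protocol 6.1.3, subjects have "a Follow-up visit within the Day 52–59 period". One group is exempt: "Subjects who stop study drug prior to Day 22 AND are considered clinical failures", failure here meaning that a change of antifungal therapy is needed. They "may have their Follow-up visit earlier, but the visit must still be" at least 30 days after the last weekly infusion. The Protocol synopsis, note c to Protocol Table 1, SAP 1.2 and SAP Appendix 2 repeat the rule.

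Protocol 7.4.2 covers subjects whose daily blood cultures stay positive through Day 7. Study drug is stopped and salvage therapy started, and: "The subject should remain in the study through the Follow-up visit (Days 52–59) to complete safety assessments and assess for mortality".

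The late survival read-outs are these:
- SAP 2.3.2: anyone without a recorded death by Day 59, including those lost before then, "will be censored in the analysis at the last date known to be alive or Day 59, whichever is earlier".
- Protocol 13.4.4: from the Kaplan-Meier analysis, "the probability of being alive at Day 5, Day 14, Day 30, and Day 55 will be determined by treatment group".
- SAP 4.3.4: a crude mITT table of "frequencies and percentage of subjects that were alive and deceased at Follow-up".

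Neither document specifies a contact after an early Follow-up visit. The sensitivity analyses in SAP 4.3.1.1 cover only the two primary outcomes.

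**The concern.** The right to shorter observation depends on a poor outcome. Kaplan-Meier assumes that subjects censored at a given day have the same later risk as those still observed. Subjects whose antifungal treatment failed may well not. If their last date known alive is an early visit, the Day 55 estimate rests on the better-risk subjects who remain.

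The crude table has a simpler weakness. It has no fixed day, so a failure seen alive on Day 31 counts as alive in the same way as a cure seen alive on Day 59.

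At stake is the reading of survival by arm between Day 30 and the end of the study.

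**Working it through.** **Days.** Last weekly infusion plus 30: 1 + 30 = 31, 8 + 30 = 38, 15 + 30 = 45, 22 + 30 = 52. Day 31 applies only if the Day 1 infusion was the last. It falls 21–28 days short of the Day 52–59 window.

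**Overlap of the two sections.** A subject with positive cultures through Day 7 stops drug before Day 22 and changes therapy, so also meets the 6.1.3 condition. If drug stops before the Day 8 infusion, 6.1.3 allows Follow-up at Day 31, while 7.4.2 asks for Days 52–59.

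**Size.** The plan states no figure for survival after Day 30, so there is none to reproduce. The inputs below are assumptions except where marked.
- Failures: 20%, 25% or 30% of mITT, paired with mortality over Days 31–59 of 15%, 20% or 25% among failures alive at Day 30. In other survivors it is 4%.
- Day 30 mortality: 35% in failures and 12% in others. This gives 16.6–18.9% overall, close to the plan's 20% (Protocol 13.8).
- Constant daily hazard over the 29 days. Early finishers are split equally over Days 31, 38 and 45, with no later status obtained.

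*Middle case in full (25% failures, 20% late mortality, all surviving failures leave early):*
- Day 30 mortality: 0.25 × 35 + 0.75 × 12 = 17.75%.
- Alive at Day 30: failures 0.25 × 65 = 16.25%; others 0.75 × 88 = 66.00%.
- Dead by Day 55 (25 of the 29 days): failures 1 − 0.80^(25/29) = 17.50%; others 1 − 0.96^(25/29) = 3.46%.
- True Day 55 mortality: 17.75 + 16.25 × 0.1750 + 66.00 × 0.0346 = 22.9%.
- Crude table: failures are seen for 1, 8 or 15 days after Day 30. Their observed death risk is the mean of 1 − 0.80^(1/29), 1 − 0.80^(8/29) and 1 − 0.80^(15/29), that is, of 0.77%, 5.97% and 10.90% = 5.88%. So 17.75 + 16.25 × 0.0588 + 66.00 × 0.0346 = 21.0%, low by 1.9 points.
- Kaplan-Meier, the daily product of (1 − deaths/at risk): 21.4%, low by 1.5 points.

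| Failures / late mortality | True | Kaplan-Meier | Crude | KM gap, all leave | KM gap, 50% leave | KM gap, 25% leave |
|---|---|---|---|---|---|---|
| 20% / 15% | 20.7 | 19.9 | 19.6 | 0.8 | 0.4 | 0.2 |
| 25% / 20% | 22.9 | 21.4 | 21.0 | 1.5 | 0.7 | 0.3 |
| 30% / 25% | 25.3 | 23.0 | 22.5 | 2.3 | 1.0 | 0.5 |

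The crude gaps with all leaving are 1.1, 1.9 and 2.8 points.

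**Same late mortality in both groups.** With 25% failures and 4% late mortality in everyone, Kaplan-Meier equals the truth (20.6%). The crude table still reads low, at 20.2%.

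**Between arms.** Suppose one arm has 10 points more failures and all surviving failures leave early. The true Day 55 difference across the three cases is 2.85, 3.13 and 3.42 points. Kaplan-Meier shows 2.46, 2.60 and 2.74; the crude table shows 2.28, 2.38 and 2.48. The loss is 0.4–0.7 points (Kaplan-Meier) or 0.6–0.9 points (crude). Of the true difference, 0.10 × (35 − 12) = 2.3 points has already arisen by Day 30.

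**Harsher case.** Let every early finisher leave on Day 31, with Day 30 mortality 20%, 5% late mortality in others, and Day 59 as the read-out. With early finishers 15% of mITT and dying at 40%, Kaplan-Meier shows 24.2% against a true 29.3%. With early finishers 15% of one arm and 5% of the other, dying at 20%, a true difference of 1.5 points shows as about 0.1. This needs every early finisher to have had only the Day 1 infusion.

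**The case against.** The strongest reply is that the documents already look for late deaths. The early visit is optional. Censoring is at the last date known alive, not at the visit. Protocol 7.4.2 calls for mortality assessment after early discontinuation of drug, and SAP 2.1 promises all attempts to establish survival at Day 30 and at Follow-up. Protocol 12.6 follows unresolved serious events, and SAP 4.5.1 counts fatal events that began during the study even when death came after the Follow-up visit. So some deaths after an early visit will reach the database.

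Much of this stands, and it is why the bias is possible rather than established. It does not close the gap. For a subject with an early visit, that visit is the Follow-up visit. The search of records in SAP 3.7 is written for the Day 30 outcome. Adverse event collection ends at Follow-up (Protocol 12.2), and after the study period only serious events believed related to the product must be notified (Protocol 12.3.1). A death on Day 45 from the underlying disease, after a Day 31 visit, has no assured route into the data.

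The objection is also right on size. The 30% non-cure rate implied by the design includes deaths, indeterminate responses, adverse-event discontinuations and unresolved signs, none of which qualifies alone for the early visit, so full uptake among 20–30% is an upper case. With 92 per group and about 23% mortality, the standard error of the difference is √(2 × 0.23 × 0.77 / 92) = 6.2 points, a 95% interval of about ±12. A shift of under 1 point would not be visible.

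**Conclusion.** The point holds as a possibility created by the wording, together with an unreconciled conflict between Protocol 6.1.3 and 7.4.2. Kaplan-Meier mortality is biased low only if sites use the option, no later status is obtained, and early finishers then die faster than others. The crude table can miss deaths under the first two conditions alone. Under the main assumed rates, Day 55 mortality is low by at most 0.8–2.3 points (Kaplan-Meier) or 1.1–2.8 points (crude), and by about 0.2–1.0 points (Kaplan-Meier) at 25–50% uptake. The distortion of the between-arm difference is under about 1 point. The Day-31-only case gives more, but rests on a more extreme pattern of exits.

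A reader might infer that late mortality will be understated, or that a late difference between arms will be diluted. The documents support neither: they give no uptake, no late mortality rates and no sign of which arm will have more failures. Nor should the whole Day 55 difference in the example be read as late, since 2.3 points of it precede Day 31.

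Both primary outcomes (Day 14 global cure and Day 30 mortality) fall before the earliest exit and are unaffected. Survival through Follow-up is listed as exploratory in SAP 2.3, with no margin or specified test. This is a cheap improvement, not a threat to the trial's conclusions.

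**What to change.** - Reconcile Protocol 6.1.3 with 7.4.2, so that a subject who meets both conditions has one stated end of follow-up.
- Keep the early visit if wanted, but collect vital status by phone or records at Days 52–59 for every subject who had one.
- State in SAP 2.3.2 and 4.3.4 that this status is used in the Kaplan-Meier analysis and in the Follow-up mortality table.

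The cost is one extra contact for the subjects concerned and a few lines of protocol and SAP text.
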